8.1.3 Responder outcome for POS frequency

Responders over the On Treatment Period are defined as subjects with a 50% or greater reduction in 28-day adjusted POS frequency from Baseline to the On Treatment Period. A similar calculation applies to each 3-month time interval over the On Treatment Period and for the cohort interval for each exposure duration cohort.

The number and percentage of responders for POS frequency will be summarized for the On Treatment Period, and by 3-month time intervals over the On Treatment Period. The summary over the On Treatment Period will include all subjects in the POS Efficacy Analysis Set. Similar summaries will be provided over the full cohort interval and by 3-month time intervals for each exposure duration cohort. Responder rates for POS frequency will be summarized in the same manner by geographic region.

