6.2 Secondary Objective

- To evaluate the maintenance of efficacy over time of brivaracetam (for POS/PGS subjects)

No efficacy objectives are defined for ULD subjects or subjects coming from N01315.

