2.1.2 Secondary objectives

To evaluate the maintenance of efficacy over time of BRV (for subjects with partial onset seizures [POS] and subjects with primary generalized seizures [PGS])

No secondary efficacy objectives are defined for subjects with Unverricht-Lundborg Disease (ULD) or subjects entering the study from N01315.

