2.3 Study Design and Conduct

This is an open-label, long-term follow-up, multicenter, noncomparative, single-arm study of BRV. The primary objective is to evaluate the long-term safety and tolerability of BRV at individualized doses up to a maximum of 200mg/day in subjects with epilepsy. The secondary objective is to evaluate the maintenance of efficacy of BRV. Exploratory objectives are to assess the effects of BRV on subjects' HRQoL, obtain information on the direct and indirect costs, and explore changes in socio-professional status.

N01125 enrolled subjects 16 years of age and older who had completed N01114, N01252 (non-Indian subjects only), N01254 (non-Indian subjects only), N01187, or N01236. N01114 and N01252 enrolled subjects with focal-onset seizures with or without secondary generalization (designated as "POS subjects"). N01254 enrolled subjects with focal-onset epilepsy and a smaller number of subjects with generalized epilepsy (designated as "PGS subjects"). N01187 and N01236 enrolled subjects with ULD. Subjects entering the study from long-term follow-up study (N01315) were 16 years of age and older with from POS.

Subjects from double-blind, placebo-controlled studies N01114, N01187, and N01236 were to enter N01125 at a dose of 100mg/day after completion of a blinded Conversion Period. Subjects from double-blind, placebo-controlled N01252 were to enter N01125 at a dose of

50mg/day. The starting doses for subjects from double-blind, placebo-controlled, flexible-dose study N01254 were based on the blinded dose levels achieved during the Maintenance Period of N01254 but were not to exceed 100mg/day; thus, starting doses for subjects from N01254 were 20mg/day, 50mg/day, or 100mg/day, with most subjects entering N01125 at a dose of 100mg/day.

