3.6 Treatment Assignment and Treatment Groups

This is an uncontrolled study in which all subjects receive BRV in doses that are optimally adjusted for each subject. Generally, statistical summaries will present all subjects combined as a single treatment arm unless otherwise indicated.

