4.8 Examination of subgroups

Selected summaries will be provided for the following subgroups as specified within each of the following sections:

- Two mappings of countries to regions are defined, 1 based on the classification requested by Food and Drug Administration (FDA), and 1 based on the regional classification for the CHMP (Committee for Medicinal Products for Human Use).

Countries will be mapped to geographic regions as follows for the FDA:

Geographic Region (FDA)	Country
North America	Canada, United States, Puerto Rico
Latin America	Brazil, Mexico
Western Europe	Austria, Belgium, Finland, France, Germany, Ireland, Italy, Netherlands, Norway, Réunion, Spain, Sweden, United Kingdom, Switzerland
Eastern Europe	Bulgaria, Czech Republic, Estonia, Latvia, Hungary, Lithuania, Poland, Romania, Russia, Serbia and Montenegro, Turkey, Ukraine
Asia/Pacific/Other	Australia, Hong Kong, India, Israel, Japan, Singapore, South Africa, Republic of Korea, Taiwan, Tunisia

Countries will be mapped to geographic regions as follows for the CHMP:

Geographic Region (CHMP)	Country
North America	Canada, United States, Puerto Rico
Latin America	Brazil, Mexico
Europe (European Union [EU] member states) *	Austria, Belgium, Bulgaria, Czech Republic, Estonia, Finland, France, Germany, Hungary, Ireland, Italy, Latvia, Lithuania, Netherlands, Norway, Poland, Réunion, Romania, Spain, Sweden, United Kingdom
Europe (non-EU member states)	Russia, Serbia and Montenegro, Switzerland, Turkey, Ukraine
Asia/Pacific/Other	Australia, Hong Kong, India, Israel, Japan, Singapore, South Africa, Republic of Korea, Taiwan, Tunisia

* EU member states plus Norway.

- Indication (Partial Onset Seizures, Primary Generalized Seizures, ULD)
- Randomized treatment in the previous study (placebo [PBO], BRV)

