8.1.2 Percent reduction in POS frequency

Percent reduction in POS frequency from Baseline to the On Treatment Period will be calculated as follows, where On Treatment Period Frequency is the 28-day adjusted POS frequency during On Treatment Period and Baseline Period Frequency is the 28-day adjusted POS frequency during the Baseline Period of the previous study.

$$\% \text{ Reduction} = 100 \times \frac{\text{Baseline Period Frequency} - \text{On Treatment Period Frequency}}{\text{Baseline Period Frequency}}$$

A similar calculation applies to each 3-month time interval over the On Treatment Period and for the cohort interval for each exposure duration cohort.

Percent reduction from Baseline for POS frequency will be summarized with quantitative descriptive statistics for the On Treatment Period, and by 3-month time intervals over the On Treatment Period. The summary over the On Treatment Period will include all subjects in the POS Efficacy Analysis Set. Similar summaries will be provided for the full cohort interval and by 3-month time intervals for each exposure duration cohort. Percent reduction from Baseline for POS frequency will be summarized in the same manner by geographic region.

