11.2.2 General summaries of TEAEs

Pre-treatment AEs will be provided in a subject data listing; no summaries of pre-treatment AEs are planned.

An overall summary of AEs will provide the overall number of TEAEs and the numbers and percentages of subjects with at least 1 TEAE, with a TEAE that led to permanent discontinuation of study drug, with a drug-related TEAE, with a severe TEAE, with a treatment-emergent SAE, and with a drug-related treatment-emergent SAE. The number and percentage of subjects who died will also be summarized. This summary will be provided for all subjects in the Safety Analysis Set and also by subgroup for geographic region and indication.

The following summaries of TEAEs will be provided by MedDRA SOC and PT. All summaries are for the combined Evaluation, Down-Titration, and Post-Treatment Periods unless otherwise indicated.

Overall Incidence Summaries

- Incidence of TEAEs
- Incidence of TEAEs by 3-month time interval
- Incidence of TEAEs by study period (Evaluation, Down-Titration, Post-Treatment)
- Incidence of TEAEs for TEAEs occurring in at least 5% of subjects

- Incidence of TEAEs by 3-month time intervals for TEAEs occurring in at least 5% of subjects overall
- Incidence of non-serious TEAEs occurring in at least 5% of subjects

The incidence of TEAEs occurring in at least 5% of subjects will be summarized overall as noted above and also by subgroup for geographic region, indication, and randomized treatment from the previous double-blind study.

A subject is included in a 3-month interval if the subject was receiving BRV at any time during that interval based on their duration of exposure to BRV (eg, a subject with exposure for 91 days is included in the time interval for Months 1-3 and Months 4-6). Summaries of AEs by 3-month intervals will include all subjects who are classified into each time interval as defined above. TEAEs which had onset prior to or on the date of the last dose of BRV are included in summaries by 3-month time intervals.

Maximum Intensity and Causality

- Incidence of TEAEs by maximum intensity
- Incidence of drug-related TEAEs

Serious Adverse Events

- Incidence of treatment-emergent SAEs

Discontinuations due to TEAE

- Incidence of TEAEs leading to permanent discontinuation of study drug

TEAEs of interest

AEs of interest will be identified based on MedDRA search criteria, which are documented outside of the SAP. The following summaries will be provided for AEs of interest:

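### The efficacy-over-time tables pool former placebo and former brivaracetam subjects, so first response in one group can offset early loss of effect in the other and dilute it later

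*SAP*

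**What the plan says.** Protocol 6.2 sets the objective: "To evaluate the maintenance of efficacy over time of brivaracetam (for POS/PGS subjects"). SAP 2.1.2 repeats it.

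SAP 3.6 gives the default display: "Generally, statistical summaries will present all subjects combined as a single treatment arm unless otherwise indicated". SAP 8.1.1 to 8.1.3 then summarise partial onset seizure (POS) frequency, percent reduction and responder rate over the On Treatment Period, by 3-month interval and by exposure duration cohort. For percent reduction the only subgroup is regional: "Percent reduction from Baseline for POS frequency will be summarized in the same manner by geographic region". SAP 8.1.3 says the same of the responder rate: "Responder rates for POS frequency will be summarized in the same manner by geographic region". SAP 8.2.2.1 to 8.2.2.3 handle PGS seizure days in the same way.

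The clock starts at the first BRV dose in N01125 (SAP 3.2.1, 3.2.5). Baseline is that of the previous study for everyone (SAP 3.3).

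SAP 4.8 lists a further subgroup: "Randomized treatment in the previous study (placebo [PBO], BRV"). The only display that uses it is the table of treatment-emergent adverse events in at least 5% of subjects, produced "also by subgroup for geographic region, indication, and randomized treatment from the previous double-blind study" (SAP 11.2.2).

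**The concern.** The early intervals mean different things for different subjects. For a former placebo subject from N01252 or N01254, Months 1-3 hold the first response to BRV. For a former BRV subject they are a continuation of treatment. Both are measured against a pretreatment baseline and averaged in one column.

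A level pooled curve could therefore come from stable effect in both groups, or from improvement in one and loss in the other. No hypothesis test is planned (SAP 3.1), so these tables are the whole of the evidence on the objective. The variable that would separate the two explanations is already defined, but no efficacy table uses it.

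**Working it through.** **Who starts BRV when.**

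- *N01252.* Protocol 5.3 lists doses of 20, 50 and 100 mg/day, and the study was placebo-controlled. SAP 2.3 gives one entry dose for all: "Subjects from double-blind, placebo-controlled N01252 were to enter N01125 at a dose of" 50 mg/day. SAP 3.2.3 has subjects who enter immediately coming from the Treatment Period. I infer that former placebo subjects start BRV at about Day 1. Of the three BRV arms, the 20 and 100 mg/day arms change dose at entry.
- *N01254.* Entry is also from the Treatment Period, at a dose based on the blinded level reached, up to 100 mg/day. The same inference applies to its placebo subjects.
- *N01114.* Subjects enter at 100 mg/day after a blinded Conversion Period (SAP 2.3, 3.2.3). Nothing describes its former placebo subjects as starting BRV on Day 1.

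**Whether another display separates the groups.** Exposure duration cohorts are built from N01125 exposure alone (SAP 3.2.1, 3.2.7). SAP 4.2 gives their purpose as removing the influence of earlier discontinuations. Each cohort can still contain both former placebo and former BRV subjects.

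**Size of the possible offset.** The plan has no figure of its own to reproduce. Let w be the former placebo share. Then:

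- pooled rate = w × (former placebo rate) + (1 − w) × (former BRV rate)
- pooled change = w × rise − (1 − w) × fall
- fall fully hidden by a given rise = w / (1 − w) × rise

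The documents give neither w nor any responder rate for this study. I assume w from 20% to 50%. Results are in percentage points between two intervals:

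| w | Former BRV fall fully hidden by a 10-point former placebo rise | Pooled change: fall of 10, rise of 10 | Pooled change: fall of 10, former placebo flat |
|---|---|---|---|
| 20% | 0.20/0.80 × 10 = 2.5 | 2.0 − 8.0 = −6.0 | −8.0 |
| 25% | 0.25/0.75 × 10 = 3.3 | 2.5 − 7.5 = −5.0 | −7.5 |
| 33% | (1/3)/(2/3) × 10 = 5.0 | 3.3 − 6.7 = −3.3 | −6.7 |
| 50% | 0.50/0.50 × 10 = 10.0 | 5.0 − 5.0 = 0.0 | −5.0 |

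An example with assumed rates: former BRV responders fall from 40% to 30% while former placebo responders rise from 20% to 40%. At w = 25% the pooled rate goes from 0.25 × 20 + 0.75 × 40 = 35.0% to 0.25 × 40 + 0.75 × 30 = 32.5%. At w = 1/3 it is 33.3% in both intervals. A split table would show −10 and +20 directly.

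**The case against.** The study is uncontrolled and descriptive, efficacy is not its primary objective (SAP 4.2), and pooling is the declared default. No statement in the plan is contradicted. That is so, and it makes this a missing display, not an error.

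The timing argument is stronger. Full masking needs former placebo subjects to keep improving from one interval to the next. The first interval spans 90 days. If onset is complete by then, later intervals show any loss in diluted form, and within an exposure cohort they follow the same subjects. The visits taken as study entry are at Week 12 for N01252 and Week 16 for N01254 (SAP 3.2.3), whereas retention is to be estimated out to 60 months (SAP 5.1). This stands: the problem lies mainly in the early intervals. It does not vanish after them, because BRV dose and concomitant antiepileptic drugs may be adjusted throughout (SAP 2.3), so further change after Month 3 is possible, and dilution still understates a loss.

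It is also fair that former BRV subjects are not a clean durability group. Some from N01252 change dose at entry, some subjects had a treatment gap (SAP 3.2.3), and co-medication can change. Neither document confines the objective to them, and former placebo subjects followed for years after responding inform it too. The split reduces the mixing but does not isolate pure durability.

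**Conclusion.** The point holds as a gap worth closing. No efficacy-over-time table is split by previous randomised treatment, although the subgroup exists and prior exposure bears directly on the objective. With an assumed former placebo share of 20% to 50%, a 10-point rise in that group fully hides a former BRV fall of 2.5 to 10 points. With no rise, a 10-point fall appears as 8 to 5 points.

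A reader might infer three stronger things that the documents do not support:

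- *Maintenance cannot be read at all.* Later intervals would still show a loss, only smaller.
- *Every former placebo subject starts on Day 1.* That follows for immediate entrants from N01252 and N01254, not for N01114.
- *A loss is in fact being hidden.* The shares and rates are assumptions. They show that masking is possible, not that it is likely.

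**What to change.** In SAP 8.1.1 to 8.1.3 and 8.2.2.1 to 8.2.2.3, repeat the On Treatment, 3-month-interval and exposure-cohort summaries by previous randomised treatment (placebo, BRV) as defined in SAP 4.8. Show N01114 separately, or footnote its Conversion Period. State that maintenance in the early intervals is interpreted primarily from the previously BRV-randomised group, and note that some of them changed dose at entry.

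A reference column with that group's response in the feeder study's treatment period would help but is optional. The SAP takes feeder-study seizure data only for Baseline (SAP 3.3, 3.8.1), so the column needs an added derivation.

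The split itself needs no new data, since the variable is already required for the adverse event table. The cost is extra tables and smaller denominators, with less precise percentages, mainly for PGS.

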8.2 Analysis of other efficacy variables

8.2.1 Subjects with partial onset seizures

All of the following variables are summarized for the Efficacy Analysis Set for POS.

8.2.1.1 Specified Month seizure freedom

The numbers and percentages of subjects who are seizure free for all seizure types for any continuous 6-month interval, 12-month interval, 18-month interval, and so forth will be summarized overall for the period of time that subjects are being treated with BRV and by Exposure Duration Cohort. The overall summary will present the number and percentage of subjects who reported no seizures for the specified duration of seizure freedom and the seizure diary was completed for at least 90% of days within the seizure-free interval. Subjects whose duration of BRV treatment was less than the specified duration of seizure freedom will be considered failures for seizure-freedom. Summaries by exposure duration cohort will present the number and percentage of subjects who reported no seizures for the specified duration of seizure freedom at any time during the cohort interval (eg, through the end of Month 6 for the 6-month cohort) and the seizure diary was completed for at least 90% of days within the seizure-free interval. Percentages are relative to the number of subjects within each Exposure Duration Cohort.

A subject is seizure free for a 6-month interval if the subject did not report any seizures in the 6-month interval and the seizure diary was completed for at least 90% of days within the seizure-free interval. The percentage of days for which seizure diary was completed within a given 6-month interval will be calculated as follows based on a 30-day month:

$$\% \text{ of days diary was done} = 100 \times \left[\frac{180 - \text{number of days diary was not done in the interval}}{180} \right]$$

A similar calculation applies for 12-month seizure freedom based on 360 days, 18-month seizure freedom based on 540 days, and so forth.

8.2.2 Subjects with Primary Generalized Seizures

The following variables are summarized for the Efficacy Analysis Set for PGS.

8.2.2.1 All type seizure days

Twenty-eight day adjusted all other type seizure days will be summarized with quantitative descriptive statistics in the same manner as 28-day adjusted POS frequency.

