No secondary efficacy variables are defined for subjects with generalized epilepsy, subjects with Unverricht-Lundborg Disease (ULD), or subjects coming from N01315.

- Other efficacy variables

For subjects with focal-onset epilepsy:

This document cannot be used to support any marketing application and any extensions or variations thereof.

- o Percentage of subjects continuously seizure free for all seizure types (I+II+III) for at least 6 months and at least 12 months during the Evaluation Period.

For subjects with generalized epilepsy:

- o Generalized (type II) seizure days per 28 days during the Evaluation Period.
- o Percent reduction in generalized (type II) seizure days per 28 days from Baseline of the previous study to the Evaluation Period.
- o Responder rate for generalized (type II) seizure days over the Evaluation Period. A responder is defined as a subject with a $\geq 50\%$ reduction in seizure days from the Baseline Period of the previous study.
- o Percentage of subjects continuously seizure free for all seizure types (I+II+III) for at least 6 months and at least 12 months during the Evaluation Period.

The following will be evaluated separately for subjects with focal-onset epilepsy and subjects with generalized epilepsy:

- o Change in Patient Weighted Quality of Life in Epilepsy Questionnaire (QOLIE-31-P) scores from Baseline of the previous study to each assessment for the first 2 years and to the last Evaluation Period assessment during the first 2 years.
- o EuroQol 5 Dimensions (EQ-5D) Questionnaire response for each assessment for the first 2 years for the Evaluation Period and for the last assessment during the first 2 years of the Evaluation Period.

No other efficacy variables are defined for subjects with ULD or coming from N01315.

Pharmacoeconomic variables

The following will be evaluated separately for subjects with focal-onset epilepsy and subjects with generalized epilepsy:

- Direct costs (healthcare provider consultations not foreseen by the protocol, concurrent medical procedures, concomitant medications, hospitalizations, and emergency room visits) during the first 2 years of the Evaluation Period
- Indirect costs (work days or school days lost by the subject and days subject received help from a caregiver) during the first 2 years of the Evaluation Period
- Socio-professional data for each assessment for the first 2 years and for the last assessment during the first 2 years of the Evaluation Period

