2.2.2.2 Other efficacy variables

For subjects with focal-onset epilepsy:

- Percentage of subjects continuously seizure-free for all seizure types (I+II+III) for at least 6 months and at least 12 months during the Evaluation Period

For subjects with generalized epilepsy:

- Generalized (type II) seizure days per 28 days during the Evaluation Period
- Percent reduction in generalized (type II) seizure days per 28 days from Baseline of the previous study to the Evaluation Period
- Responder rate for generalized (type II) seizure days over the Evaluation Period. A responder is defined as a subject with a $\geq 50\%$ reduction in seizure days from the Baseline Period of the previous study.
- Percentage of subjects continuously seizure-free for all seizure types (I+II+III) for at least 6 months and at least 12 months during the Evaluation Period

The following will be evaluated separately for subjects with focal-onset epilepsy and subjects with generalized epilepsy:

- Change in Patient Weighted Quality of Life in Epilepsy Questionnaire (QOLIE-31-P) scores from Baseline of the previous study to each assessment for the first 2 years and to the last Evaluation Period assessment during the first 2 years
- EuroQol 5 Dimensions (EQ-5D) questionnaire response for each assessment for the first 2 years for the Evaluation Period and for the last assessment during the first 2 years of the Evaluation Period

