3.8.1.3 Calculation of adjusted seizure days

The following derivations apply only to subjects with Primary Generalized Seizures, based on the 1981 ILAE classification, Primary Generalized Seizures include the generalized seizure types and unclassified seizure types.

Baseline seizure days for seizure types II, IIA through IIF, and for all seizure types (I+II+III) will be obtained from the Baseline Period of the previous study.

The total number of seizure days for seizure types II, IIA through IIF, and the total number of seizure days for all seizure types (I+II+III) will be calculated overall, by 3-month time intervals, and over the cohort interval for each exposure duration cohort. The same seizure diary data defined in the Section 3.8.1.2 for POS frequency will be considered.

Twenty-eight day adjusted seizure days for seizure types II, IIA through IIF, and for all seizure types (I+II+III) will be calculated overall, within each 3-month time interval, and over each exposure duration cohort interval by dividing the total number of seizure days for

each seizure type by the number of days for which the diary was completed overall (ie, over the periods defined in the Section 3.8.1.2), within each 3-month interval, and within each exposure duration cohort interval, and multiplying the resulting value by 28.

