8 EFFICACY ANALYSES

In general, all study outcomes based on seizure frequency will be summarized for the Efficacy Analysis Set for POS and all study outcomes based on seizure days will be summarized for the Efficacy Analysis Set for PGS. No efficacy summaries are provided for ULD subjects or subjects entering the study from N01315.

The derivations of 28-day adjusted seizure frequency and 28-day adjusted seizure days are described in detail in Section 3.8.1.2 and Section 3.8.1.3, respectively.

All summaries of efficacy data are descriptive; no statistical testing will be performed.

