8.2.2.2 Percent reduction in all type seizure days

Percent reduction in all other type seizure days from Baseline will be calculated in the same manner as percent reduction in POS frequency as described in Section 8.1.2. This variable will be summarized in the same manner as percent reduction in POS frequency.

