8.2.2.3 Responder outcome for all type seizure days

Responder outcome for all other type seizure days will be derived in a manner similar to the responder outcome for POS frequency as described in Section 8.1.3. This variable will be summarized in the same manner as 50% responder outcome for POS frequency.

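### SAP 8.2.2.1 to 8.2.2.3 plan all-type seizure-day summaries for generalized epilepsy, although the three variables concerned are defined on type II seizure days

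*SAP*

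**What the plan says.** **Definitions.** SAP 2.2.2.2 lists, for generalized epilepsy, "Generalized (type II) seizure days per 28 days during the Evaluation Period", followed by the percent reduction and the responder rate, both also on type II days. Protocol 13.1.2.2 has the same list, and so does the Protocol Summary (section 4), for example "Percent reduction in generalized (type II) seizure days per 28 days from Baseline of the previous study to the Evaluation Period". A fourth variable, continuous seizure freedom, is defined in the same lists on all seizure types (I+II+III).

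**Derivation.** SAP 3.8.1.3 states: "Twenty-eight day adjusted seizure days for seizure types II, IIA through IIF, and for all seizure types (I+II+III) will be calculated overall". These are the only seizure-day quantities it derives. It also remarks that "Primary Generalized Seizures include the generalized seizure types and unclassified seizure types".

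**Planned analysis.** SAP section 8 says that, in general, "all study outcomes based on seizure days will be summarized for the Efficacy Analysis Set for PGS". The specific text is in 8.2.2.1 to 8.2.2.3. All three headings, and the SAP contents list, say *all type*. The text under them reads:

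- 8.2.2.1: "Twenty-eight day adjusted all other type seizure days will be summarized with quantitative descriptive statistics"
- 8.2.2.2: "Percent reduction in all other type seizure days from Baseline will be calculated"
- 8.2.2.3: "Responder outcome for all other type seizure days will be derived"

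The methods are taken by reference from the partial-onset subsections 8.1.1 to 8.1.3.

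**The concern.** The analysis subsections do not name the variable they are meant to analyze. Type II appears in the definitions and in the derivation but is absent from 8.2.2.1 to 8.2.2.3, whose headings and text also disagree with each other. A programmer who follows section 8.2.2 literally would tabulate something other than the defined variables, and two programmers might tabulate different things.

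The secondary objective, maintenance of efficacy over time, covers subjects with generalized epilepsy (Protocol 6.2, SAP 2.1.2), yet SAP 2.2.2.1 defines no secondary efficacy variable for them. Their seizure evidence therefore comes from four variables in the *other* category, and three of the four are affected.

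**Working it through.** **1. The passages side by side**

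| Place | Days per 28 days | Percent reduction | Responder |
|---|---|---|---|
| Protocol 4, Protocol 13.1.2.2, SAP 2.2.2.2 | type II | type II | type II |
| SAP 3.8.1.3 | II, IIA to IIF; I+II+III | none | none |
| SAP 8.2.2.1 to 8.2.2.3, headings | all type | all type | all type |
| SAP 8.2.2.1 to 8.2.2.3, text | all other type | all other type | all other type |

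The phrase *all other type* occurs only in these three subsections and is not defined. The headings match one of the two families derived in 3.8.1.3, namely I+II+III. The best-supported reading is therefore I+II+III with a stray *other*. Deleting that word would make headings and text agree, but on a variable that is not the defined one.

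Nothing suggests a deliberate change. The definition lists keep type II apart from I+II+III, which they use only for seizure freedom. The seven changes in SAP section 14 include no move from type II to all types.

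**2. How far I+II+III can depart from type II**

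The plan gives no figure to reproduce. Apply the percent-reduction formula of SAP 8.1.2 to one subject, counting a type II day as any day with at least one type II seizure. Then all-type days are type II days plus days with seizures but none of type II. Let *f* be the share of Baseline all-type days that have no type II seizure. For *f* above zero:

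all-type reduction = (1 − *f*) × type II reduction + *f* × reduction in the days without a type II seizure

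If *f* is zero and no such days appear on treatment, the two reductions are equal. If such days appear only on treatment, the all-type reduction is the lower one.

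The documents give neither *f* nor the number of subjects with generalized epilepsy, so the inputs below are assumptions that show direction only.

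*Type II reduction 60%, other days unchanged:* all-type reduction = 60% × (1 − *f*).

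| *f* | 0% | 5% | 10% | 15% | 20% | 30% |
|---|---|---|---|---|---|---|
| All-type reduction | 60% | 57% | 54% | 51% | 48% | 42% |

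It falls below the 50% responder threshold once *f* exceeds 1 − 50/60 = 16.7%. With a type II reduction of 80%, the corresponding value is 1 − 50/80 = 37.5%.

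*Other days fall in proportion to type II days:* no difference, whatever *f* is. If they fall by more, the all-type reduction is the larger one.

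*One assumed subject:* type II days go from 10 to 4, type III-only days stay at 1, and type I-only days stay at 2.

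- Type II: (10 − 4)/10 = 60.0%, responder.
- I+II+III: (13 − 7)/13 = 46.2%, non-responder.
- I+II+III without the type I-only days: (11 − 5)/11 = 54.5%, responder.

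The choice of variable can change a subject's responder status, but it need not.

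**The case against.** The strongest reply is that the gap is small. The SAP lists the type II variables. It derives type II days at Baseline and on treatment, overall, by 3-month interval and by exposure cohort. It supplies the percent-reduction and responder methods by cross-reference, and section 8 promises summaries of seizure-day outcomes for this group. On that view only the name of the seizure type is missing from three subsections. This stands as a description of the repair. It does not remove the mismatch: the general sentence in section 8 names no type, a derivation is not a planned summary, and the specific subsections point to another variable.

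It is also fair to say that the responder switch in the example depends on type I-only days. These may be rare in subjects with a generalized diagnosis, and without them that subject remains a responder at 54.5%. The true difference could be nil.

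Two stronger readings are tempting. A reader might infer that *all other type* means every type except II. Percent reduction would then be undefined for anyone with only type II seizures at Baseline. The documents do not support this: it contradicts the three headings, has no derivation in 3.8.1.3, and would discard the generalized seizures of the generalized-epilepsy group. A reader might instead infer types II+III from the remark in 3.8.1.3 about unclassified seizures. No II+III quantity is derived there, and the headings say *all type*.

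**Conclusion.** The mismatch is real and follows from the text alone. Three variables are defined on type II seizure days, the subsections that should analyze them say *all type* or an undefined *all other type*, and no section specifies a type II summary, percent reduction or responder outcome. The numerical effect is unknown and may be zero, because it depends on how many seizure days lack a type II seizure. Every percentage in the check rests on assumed inputs.

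Impact is low. All summaries are descriptive with no hypothesis testing (SAP 3.1), subjects with generalized epilepsy are a minority (Protocol 5.6), and no primary or safety conclusion is affected. The wording should still be corrected, since as written the plan does not deliver what it defines.

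A reader might infer that the fourth variable, seizure freedom, fully matches its definition. It matches on seizure type only. SAP 2.2.2.2 refers to the Evaluation Period, whereas SAP 8.2.1.1, which 8.2.2.4 follows, uses the time treated with brivaracetam. The same difference in period reaches 8.2.2.1 to 8.2.2.3 through the On Treatment Period of 8.1.1 to 8.1.3, so naming type II settles the seizure type but not the period.

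**What to change.** In the headings and text of SAP 8.2.2.1 to 8.2.2.3, write *generalized (type II) seizure days*, refer to the type II derivation in 3.8.1.3, and delete *all other type*. Any I+II+III seizure-day table may be kept as an additional summary under that name.

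If the sponsor intends I+II+III, change SAP 2.2.2.2 to match and state in the SAP that this departs from the protocol definition.

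The cost of the first option is wording in three subsections and the matching contents entries. The type II derivation already exists, so no new data or derivation is needed.
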